5. AMENDMENTS AND UPDATES

| Number | Date | Section of study protocol | Amendment or update | Reason |
|---------------|------------------|----------------------------------|----------------------------|--|
| 1 | 25 November 2019 | 1. Abstract 2. Section 9.2.2 | Amendment | 1. Revised typos from LABA/LABA to LABA/LAMA |

Proprietary confidential information © 2019 Boehringer Ingelheim International GmbH or one or more of its affiliated companies

6. MILESTONES

| Milestone | Planned Date |
|-------------------------------------|---------------------|
| IRB/IEC approval | 31 July 2019 |
| Start of data collection | 01 August 2019 |
| End of data collection | 30 November 2019 |
| Registration in the EU PAS register | 31 July 2019 |
| Final report of study results: | 31 January 2020 |

7. RATIONALE AND BACKGROUND

Chronic obstructive pulmonary disease (COPD) is a common, worldwide, and irreversible obstructive airway disease due to chronic inflammation in alveoli or airway. Generally, COPD manifests in males over 40 years and gradually progresses their health status even under the treatments. However, the steady increase prevalence in females or young patients is also found based on previous studies,^{2,3} which implies that those already known risk factors (i.e., smoking, exposure to biomass fuel or chemical particles) should be emphasized. According to the report of World Health Organization (WHO),⁴ COPD is the third leading cause of death begetting 1.7 million of death in 2016; meanwhile, it is the fifth cause of burden of disease in 2010 around the world.⁵ The global prevalence of COPD cannot be estimated precisely because of the different approaches applied for calculation.⁶ Averagely, the estimated global prevalence of COPD is 11.7% and the highest is observed in the America region with 15.2% compared to Europe and China with 7.4% and 6.5%, respectively.^{7,8} In Taiwan, COPD is the seventh leading cause of death with the estimated prevalence of 6.1%.^{9,10}

The general diagnosis of COPD includes reviewing patients' medical history, evaluating the lung function by spirometry, and emphysema using computed tomography (CT). Exacerbation/hospitalization due to exacerbation occurring ≥ 2 times/year is a predictor for a poor prognosis and increase in mortality.^{11,12} Hence, how to prevent the exacerbation is at issue for the COPD management. For this purpose, pharmacological/non-pharmacological therapies are recommended based on the Global Initiative for Chronic Obstructive Lung Disease (GOLD) guideline (version 2017)⁶ for the prevention of COPD exacerbation and reduction of the symptoms. Long-acting bronchodilators are suitable for the maintenance therapies, including long-acting beta-agonists (LABA) alone, long-acting muscarinic antagonists (LAMA) alone, and the dual therapy (fixed-dose combination [FDC] or free combos).

A few studies show LABA/LAMA therapy, especially for tiotropium (Tio) plus olodaterol (Olo), is more effective on prevention of COPD exacerbation and improvement of the quality of life and lung function than monotherapy or placebo,^{1,13-15} along with the comparison to other dual therapies.¹⁶⁻¹⁸ In Taiwan, Tio plus Olo FDC therapy (Spiolto[®]) is on the market since 2016, but the clinical data reflecting the real-world setting on COPD patients treated with Tio plus Olo vis-à-vis those with other LABA/LAMA or LAMA therapy are limited. Therefore, a retrospective, cohort study is planned to collect the clinical outcome on the prevention of acute exacerbation between different therapies for COPD in Taiwan.

8. RESEARCH QUESTION AND OBJECTIVES

The primary objective is to understand the occurrence of COPD exacerbations in patients treated with LABA/LAMA or LAMA in the routine clinical practice in Taiwan.

The secondary objectives are to realize the clinical characteristics and prescription patterns for the COPD population in Taiwan.

9. RESEARCH METHODS

9.1 STUDY DESIGN

It is a retrospective, multi-center, cohort study to collect the data on COPD patients who were administered with LABA/LAMA (FDC or free combo) or LAMA therapy for 3 months at least prior to 30 June 2018. The patients using LABA/LAMA therapy will be enrolled regardless of new initiation or switched from other single/dual/triple treatment, whereas those using LAMA treatment will only be acceptable when LAMA is newly initiated. This study aims to estimate the occurrence of COPD exacerbation in the COPD population under the real-world practice in Taiwan. Additionally, the study also assesses outcomes of clinical characteristics and prescription patterns for patients using LABA/LAMA or LAMA. After Institutional Review Board's (IRB) permission, it will be carried out in around 12 medical centers in Taiwan and plans to collect the clinical data abstracted from the medical charts of approximately 1,800 eligible patients. The eligible patients will be separated into three cohorts based on the prescription for COPD on the index date. Cohort A includes the patients treated with Tio + Olo, cohort B is the patients treated with other LABA/LAMA therapy, and cohort C is the patients receiving LAMA treatment. No investigational or interventional treatment will be provided in the retrospective study.

The retrospective study will review medical charts of COPD patients with LABA/LAMA or LAMA therapy until death or 1 year after the index date, whichever occurs first. The data collection will be conducted after eligibility assessment. Medical records will be reviewed and relevant information will be abstracted for various details such as patient demographics, diagnosis of COPD, smoking status, records of exacerbations and hospitalization, examinations of lung function and laboratory, treatments related to COPD or comorbidities, reasons for treatment switching, and comorbidities.

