| Study design: | 
This is a retrospective, multi-center, cohort study to collect the data on COPD patients who were administered with LABA/LAMA (FDC or free combo) or LAMA treatment for 3 months at least prior to 30 June 2018. For LABA/LAMA therapy, new initiation or switching from other therapy (i.e., single/dual/triple) are both acceptable; for LAMA
 | | |

Proprietary confidential information © 2019 Boehringer Ingelheim International GmbH or one or more of its affiliated companies

| | |
|--------------------|---|
| | 
treatment, only new initiation will be acceptable. The data abstracted from eligible patients will be recorded only when they are available in the medical chart and will be categorized into the cohort A (patients treated with Tio + Olo), B (patients treated with other LABA/LAMA therapy), and C (LAMA therapy).
 
The follow-up period for each patient will be from the index date* until the date of death or 1 year after the index date, whichever occurs first. Patients will be censored at the time from one LAMA/LABA or LAMA switched to another LAMA/LABA or ICS.
 
*Index date: It is defined as the date of COPD patients in the cohort A and B starting using LABA/LAMA therapy regardless of new initiation or switching from other single/dual/triple treatment, or the date of the patients in the cohort C starting using LAMA treatment.
 |
| Population: | 
This study plans to review the medical chart from approximately 1,800 COPD patients receiving LABA/LAMA or LAMA treatment for 3 months at least prior to June 30 2018 in Taiwan.
 
Inclusion criteria
 
Patients who fulfil ALL the following criteria are included.
 
1. Patients who diagnosed with COPD who were prescribed with LABA/LAMA (FDC or free combo) as a new initiation or switching from other therapy (i.e., single/dual/triple), or newly receiving LAMA treatment for 3 months at least prior to 30 June 20182. Male or female patients ≥ 40 years of age 
Exclusion criteria
 
Patients who meet the following criterion are not included.
 
1. Patients with documented diagnosis of bronchial asthma, asthma-COPD overlap syndrome (ACOS), bronchiectasis, cystic fibrosis, or lung cancer |

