9.2.2 Study population

The data will be retrospectively abstracted from the medical chart after eligibility assessment. Eligible patients will be categorized into the cohort A (patients treated with Tio + Olo), B (patients treated with other LABA/LAMA therapy), and C (patients treated with LAMA therapy).

Inclusion criteria

Patients who fulfil **ALL** the following criteria are included.

1. Patients who diagnosed with COPD who were prescribed with LABA/LAMA (FDC or free combo) as a new initiation or switching from other therapy (i.e., single/dual/triple), or newly receiving LAMA treatment for 3 months at least prior to 30 June 2018
2. Male or female patients ≥ 40 years of age

Exclusion criteria

Patients who meet the following criterion are not included.

1. Patients with documented diagnosis of bronchial asthma, asthma-COPD overlap syndrome (ACOS), bronchiectasis, cystic fibrosis, or lung cancer

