9.7.1 Main analysis

The propensity score matching approach* will be used to balance the baseline characteristics between the study cohorts. These data will be compared descriptively between patients receiving different regimens (Tio + Olo vs. other LABA/LAMA vs. LAMA). If the propensity score matching is done, the difference before and after matching will be considered both.

For the primary outcome

Time to the first moderate or severe COPD exacerbation will be compared between different cohorts using Kaplan-Meier curves with the incidence and time to events, and statistical significance will be assessed using log-rank tests.

Time to first acute exacerbation starts from the index date to the date of the first acute exacerbation recorded on the CRF. Patients with exacerbation free at the time of escalating to ICS or no documented with exacerbations will be censored.

For secondary outcomes

- Time to escalating to dual/triple therapy will also be analysed using Kaplan-Meier curves and log-rank tests.
- The annualized rate of exacerbation with various severity will be calculated for each study group (episodes/patient-year), and the differences between the three cohorts will be compared by rate ratio.
- Results of lung function (i.e., spirometry data) and COPD assessments (i.e., CAT and mMRC) will be evaluated by the change from baseline. Pair *t*-test or other applicable statistical methods will be used for assessing the intra-group difference under a significance level of 0.05.
- Chi-square test or Fisher's exact test will be applied for categorical variables such as reasons for switching/escalating therapies, frequency, and percentage, etc.

*NOTE: Variables may include but not limited to age, gender, disease duration before index date, smoking status, body mass index, COPD assessment score (e.g., CAT and mMRC), spirometry data (e.g., FEV₁), oxygen therapy, comorbidities, disease severity, previous exacerbation, previous treatments, or eosinophil counts, where appropriate.

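### Cohorts A and B admit switchers but cohort C, on the natural reading, does not; comparisons with C should be limited to new initiators or matched exactly on initiation status

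*Combined protocol and SAP*

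**What the plan says.** The entry rule appears three times in the protocol. Section 9.1 takes LABA/LAMA patients "regardless of new initiation or switched from other single/dual/triple treatment, whereas those using LAMA treatment will only be acceptable when LAMA is newly initiated". The study design entry of the abstract (Section 4) accepts both routes for LABA/LAMA and says that for LAMA "only new initiation will be acceptable". Inclusion criterion 1 in Section 9.2.2 lists initiation or switching for LABA/LAMA, "or newly receiving LAMA treatment for 3 months at least prior to 30 June 2018". None of these places defines new initiation.

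Section 9.7 makes all eligible patients the main analysis population. In Section 9.7.1, time to first moderate or severe exacerbation is compared between cohorts by Kaplan-Meier curves and "statistical significance will be assessed using log-rank tests". For annualized exacerbation rates, "the differences between the three cohorts will be compared by rate ratio". The visible text has no restriction or stratification by initiation status.

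Confounding is to be handled by propensity score matching, which "will be used to balance the baseline characteristics between the study cohorts". The same paragraph then makes it conditional: "If the propensity score matching is done, the difference before and after matching will be considered both". The list of variables that may enter the score ends with "previous exacerbation, previous treatments, or eosinophil counts, where appropriate". No caliper is stated.

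**The concern.** The entry rule itself makes A and B differ from C in treatment history. A patient changed to LABA/LAMA from single, dual or triple therapy has, on the natural reading, no counterpart in C. Unmatched comparisons with C therefore mix regimen with treatment history.

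Matching does not clearly repair this. If prior treatment is in the score and a caliper is used, switchers tend to drop out and the estimate comes to describe new initiators, without the plan saying so. If prior treatment is left out, or there is no caliper, switchers can be paired with new starters who are unlike them.

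The objective in Section 8 is descriptive, but the primary outcome is given a significance test across cohorts. C enters that test whether it is three-way or pairwise. A significant result against C could be read as a regimen effect when it comes from the admission rule.

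**Working it through.** **Which reading of the entry rule.** The protocol sets new initiation against switching as two separate routes, so LAMA that must be newly initiated most naturally excludes switchers. Footnote 11 to Table 1 agrees: it asks for prior therapy only before LABA/LAMA. A looser reading (first LAMA prescription, other drugs possible before) would put some previously treated patients in C and make the overlap partial.

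**Inputs from the protocol.** Section 9.5: about 1,800 patients, about 300 in A and 800 in B; rates of 0.78 and 0.90 per patient-year. By subtraction, C = 1,800 − 300 − 800 = 700 (not stated). Section 9.1: at most 1 year of follow-up.

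**The plan's own figure.** Table 2, row 1, gives 0.87 (0.768, 0.978). With SE = √[1/(0.78·300·T) + 1/(0.90·800·T)]:
- T = 2 years, as stated under the table: 0.867 (0.781, 0.962).
- T = 1.5: 0.867 (0.768, 0.978), which matches the printed interval.
- T = 1: 0.867 (0.748, 1.004).

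That mismatch is a separate matter. Here 0.87 serves only as a yardstick, and 1 year per patient is used below.

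**Assumptions not in the documents.** p = switcher share of A or B, 0.3 to 0.7. m = switcher rate divided by new-starter rate, 0.8 to 1.5. f = share of log m removed by matching on the other listed variables. No drug effect.

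Apparent rate ratio against C = 1 + p(m^(1−f) − 1). For example, p = 0.7, m = 1.5, f = 0 gives 1 + 0.7 × 0.5 = 1.35; with f = 0.5, 1 + 0.7 × (1.225 − 1) = 1.16.

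The percentages are simulated log-rank rejection rates at the 5% level: exponential times, 0.90 per year in new starters, censoring at 1 year, 300 versus 300 treated as independent, 3,000 to 4,000 runs.

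| p, m | f = 0 (unmatched) | f = 0.5 | f = 0.8 |
|---|---|---|---|
| 0.3, 0.8 | 0.94; 8% | 0.97; 6% | 0.99; 5% |
| 0.7, 0.8 | 0.86; 28% | 0.93; 11% | 0.97; 7% |
| 0.3, 1.5 | 1.15; 23% | 1.07; 10% | 1.02; 6% |
| 0.5, 1.5 | 1.25; 50% | 1.11; 17% | 1.04; 6% |
| 0.7, 1.5 | 1.35; 78% | 1.16; 29% | 1.06; 9% |

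With m = 1 the rejection rate is 5%, as it should be.

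The shift can also reverse a real effect. A true ratio of 0.867 with p = 0.5 and m = 1.5 appears, unmatched, as 0.867 × 1.25 = 1.083.

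**The case against.** The best defence is that confounding control is planned. Section 9.9 acknowledges imbalance and names matching as the answer. The candidate variables include disease severity, previous exacerbation, FEV₁, CAT, mMRC and prior treatment, through which a switch history would plausibly act. If they remove 80% of the switcher effect, rejection is 5% to 9%, close to nominal. That stands as a limit on size. It does not stand as a safeguard, because prior treatment is optional, matching is conditional and unmatched differences are used as well.

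Second, new initiation is undefined, and on the looser reading C would hold some previously treated patients. That is true. It makes a common definition more necessary.

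Third, results before and after matching are both considered, so a change would be visible. The change would be seen, but not whether it came from losing switchers.

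Fourth, restriction changes the question by leaving out patients who switched, who belong to routine practice. This is fair, and it is why the all-patient results should stay as description and exact matching is offered as an alternative.

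Finally, Section 9.5 sizes only Tio + Olo against other LABA/LAMA, which share one entry rule, and the section between 9.7.1 and 9.7.3 is redacted and could hold a relevant analysis. Both are correct. The point is confined to comparisons with C in the visible main analysis.

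**Conclusion.** The concern holds. As written, the main analysis lets treatment history confound every comparison with cohort C, and on the natural reading of the entry rule no propensity score can fully repair that.

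Neither size nor direction can be derived from the documents. Over the assumed ranges, the spurious ratio is 0.86 to 1.35 unmatched, 0.93 to 1.16 if half of the switcher effect is removed, and 0.97 to 1.06 if 80% is removed. The unmatched range reaches or exceeds the planning effect of 0.87; the last range is small. Which case applies depends on how well the other variables stand in for treatment history, and the plan does not address this.

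A versus B has no structural problem, though it still needs balance on prior regimen. This is a change that should be made; confidence is medium because the definition of new initiation is open.

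**What to change.** 1. Define new initiation from the COPD medication recorded for the 6 months before the index date, and apply that definition to A, B and C alike.
2. Run A versus C and B versus C in new initiators only, or match exactly on initiation status, with a separate propensity score for each comparison.
3. Make prior regimen (none, single, dual, triple) mandatory in the A versus B score, using all patients.
4. Label unmatched all-patient comparisons with C as descriptive, without significance tests.
5. Report switchers and new initiators in each cohort, and how many of each are matched.

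**Cost.** Mainly analysis wording: Section 9.3.3.7 and the abstract's variable list already cover pre-index COPD treatment and switching. Because footnote 11 to Table 1 mentions only LABA/LAMA patients, confirm that the CRF captures the same history in C. Patients untreated for more than 6 months would count as new initiators.

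Intervals against C widen. With n matched pairs, 0.90 events per patient-year and 1 year each, the 95% limits of the rate ratio are the estimate divided and multiplied by exp(1.96·√[2/(0.90n)]). For the hazard ratio on first events, 0.90 is replaced by 1 − exp(−0.90) = 0.593. For p = 0.3, 0.5 and 0.7, A falls from 300 to 210, 150 and 90, and B from 800 to 560, 400 and 240.

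| Comparison | Pairs | Rate ratio factor | Hazard ratio factor |
|---|---|---|---|
| A vs C | 300 (no restriction) | 1.18 | 1.23 |
| A vs C | 210 / 150 / 90 | 1.22 / 1.27 / 1.36 | 1.28 / 1.34 / 1.46 |
| B vs C | 700 (the most C allows) | 1.12 | 1.15 |
| B vs C | 560 / 400 / 240 | 1.13 / 1.16 / 1.21 | 1.16 / 1.20 / 1.26 |

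These figures keep C at 700. On the looser reading the common definition would remove some C patients too, which could widen the B versus C intervals further.

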9.2 SETTING

This study plans to retrospectively collect the data abstracted from the electronic medical charts of eligible patients from around 12 medical hospitals in Taiwan.

9.2.1 Study sites

Selected sites include around 12 medical hospitals with the highest level in Taiwan from Northern to Southern area. Further, these hospitals have adequate patient pool and sufficient clinical data for collection.

9.2.2 Study population

The data will be retrospectively abstracted from the medical chart after eligibility assessment. Eligible patients will be categorized into the cohort A (patients treated with Tio + Olo), B (patients treated with other LABA/LAMA therapy), and C (patients treated with LAMA therapy).

Inclusion criteria

Patients who fulfil **ALL** the following criteria are included.

1. Patients who diagnosed with COPD who were prescribed with LABA/LAMA (FDC or free combo) as a new initiation or switching from other therapy (i.e., single/dual/triple), or newly receiving LAMA treatment for 3 months at least prior to 30 June 2018
2. Male or female patients ≥ 40 years of age

Exclusion criteria

Patients who meet the following criterion are not included.

1. Patients with documented diagnosis of bronchial asthma, asthma-COPD overlap syndrome (ACOS), bronchiectasis, cystic fibrosis, or lung cancer

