9.2.3 Study visits

The abstracted data will be recorded on the case report form (CRF). **Table 1** shows the collected data at different retrospective period of the medical chart.

Table 1 Data collection schedule

| Variables | Time points | Eligibility assessment | Data collection retrospectively | | |
|----------------------------------|-------------|------------------------|---------------------------------|-------------------------|--------------------------------------|
| | | | Before the index date | Index date [#] | 1-year follow-up period [†] |
| Eligibility assessments | X | | | | |
| Demographics ¹ | | | | X* | |
| Diagnosis of COPD ² | | | | X* | |
| Smoking status ³ | | | | X* | |
| Comorbidity ^{4, §} | | X [◊] | X | X | |
| COPD assessments [‡] | | | | | |
| CAT ⁵ | | X ^Δ | X | X | |
| mMRC ⁶ | | X ^Δ | X | X | |
| Examinations [‡] | | | | | |
| Spirometry data ⁷ | | X ^Δ | X | X | |
| Eosinophils | | X ^Δ | X | X | |
| Records [‡] | | | | | |
| Acute exacerbations ⁸ | | X ^{&} | X | X | |
| Hospital admissions ⁹ | | X ^{&} | X | X | |
| Treatments | | | | | |

| Variables | Time points | Eligibility assessment | Data collection retrospectively | | |
|--|-------------|------------------------|---------------------------------|-------------------------|--------------------------------------|
| | | | Before the index date | Index date [#] | 1-year follow-up period [†] |
| Related to COPD ^{10, \$} | | | X ^{11, ♦} | X | X |
| Related to comorbidities ^{12, \$} | | | X [◊] | X | X |
| Rescue treatments ^{13, ‡} | | | X [◊] | X | X |
| Oxygen therapy ^{14, \$} | | | X [◊] | X | X |
| Others ^{15, \$} | | | X [◊] | X | X |

[#]Not later than 30 June 2018; defined as the date of COPD patients in the cohort A and B starting using LABA/LAMA therapy regardless of new initiation or switching from other single/dual/triple treatment, or the date of the patients in the cohort C starting using LAMA treatment

[†]Not later than 1 year after the index date

^{*}The data nearest to the index date will be collected.

[◊]The data 6 months before the index date will be documented.

^{\$}The data will be collected every 6 months (allowed window: ± 1 month).

[‡]All available data on the medical chart will be recorded.

[△]The data nearest to the index date will be collected as the **Baseline**.

[&]The data/events ever since patients started receiving LABA/LAMA or LAMA therapy will be collected (maximum: trace back to 1 year before the index date).

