9.3.2.2 Secondary outcomes

- Annualized rate of mild/moderate/severe exacerbation
- Time/reason (e.g., severe airflow limitation, diagnosis of asthma, worsening exacerbation) from LABA/LAMA escalating to LABA/LAMA/ICS or from LAMA to dual therapy

Proprietary confidential information © 2019 Boehringer Ingelheim International GmbH or one or more of its affiliated companies

- Percentage of patients receiving LABA/LAMA switched to triple therapy or LAMA switched to dual therapy
- Change in pulmonary function after LABA/LAMA or LAMA initiation
- Use of rescue medications

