9.3.3 Covariates

9.3.3.1 Eligibility assessments

The eligibility should be checked by investigators before the data collection (see **Section 9.2.2** in detail). The following assessments are conducted to determine the eligibility for each patient:

1. Review the medical chart to confirm if a subject with COPD were prescribed with LABA/LAMA or LAMA therapy for 3 months at least (not later than 30 June 2018). Additionally, a subject must be ≥ 40 years of age.
2. Check the medical chart to exclude the patient with bronchial asthma, ACOS, bronchiectasis, cystic fibrosis, or lung cancer

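### The exclusion for asthma, ACOS, bronchiectasis, cystic fibrosis or lung cancer has no date limit: read literally, it selects on post-index diagnoses and conflicts with asthma as a named escalation reason

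*Combined protocol and SAP*

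**What the plan says.** Section 9.2.2 has a single exclusion criterion: "Patients with documented diagnosis of bronchial asthma, asthma-COPD overlap syndrome (ACOS), bronchiectasis, cystic fibrosis, or lung cancer". The abstract repeats it, and Section 9.3.3.1 turns it into an instruction to sites: "Check the medical chart to exclude the patient with bronchial asthma, ACOS, bronchiectasis, cystic fibrosis, or lung cancer". None of the three places gives a date limit or a look-back window. The 30 June 2018 date in these sections belongs to the treatment criterion, not to the exclusion.

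On timing, Section 9.3.3.1 states: "The eligibility should be checked by investigators before the data collection". The Table 1 footnote in Section 9.2.3 limits the index date: "Not later than 30 June 2018". Section 9.1 has charts reviewed "until death or 1 year after the index date, whichever occurs first". Section 6 plans data collection from "01 August 2019"; the abstract says July 2019.

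On outcomes, Section 9.3.2.2 (and the abstract) lists: "Time/reason (e.g., severe airflow limitation, diagnosis of asthma, worsening exacerbation) from LABA/LAMA escalating to LABA/LAMA/ICS or from LAMA to dual therapy". Section 9.7 restricts the main analysis population to patients who meet no exclusion criterion. Section 9.7.1 plans chi-square or Fisher's exact tests of escalation reasons.

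**The concern.** Cohort entry should depend only on what was known at the index date. An exclusion applied to a chart that already holds the follow-up year can remove a patient for something that happened, or was discovered, after treatment began. Such patients may have done badly or been investigated further, so their exacerbation risk need not match that of the patients who remain.

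Two things would be at stake. The primary objective is the occurrence of exacerbations, so selective removal would distort the absolute rates. If removal also differs between Tio + Olo, other LABA/LAMA and LAMA patients, the cohort comparisons would be distorted too. Propensity score matching works on baseline variables and cannot undo selection on later diagnoses.

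The loss is also hard to repair afterwards. Section 9.2.2 has data abstracted only after eligibility is settled, so an excluded patient leaves no data. The comorbidities of interest listed in Section 9.3.3.2 do not name asthma, bronchiectasis or lung cancer, so a later diagnosis may not be captured even for a patient who is kept.

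Elsewhere the protocol sets windows with care: 6 months before index for comorbidities, 1 year before index for exacerbations, and the value nearest to index for baseline tests. The exclusion has none.

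**Working it through.** The plan gives no figure on this point, so the check is of the timeline and the text, followed by an illustration on assumed inputs.

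**1. Timeline.** Latest index date 30 June 2018 + 1 year = 30 June 2019. Data collection starts in July 2019 (abstract) or on 1 August 2019 (Section 6). Both are later, so each patient's follow-up year is complete before abstraction is planned to begin.

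**2. Texts side by side.**
- Sections 9.2.2 and 9.3.3.1, read literally: a documented asthma diagnosis at any time means the patient is out.
- Section 9.3.2.2: asthma diagnosed during follow-up is an example of a reason for escalation, among patients who are in.
- Section 9.7: only patients with no exclusion criterion are analysed.

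These cannot all hold under the literal reading. They are compatible if the exclusion means a diagnosis at or before index, but no section says so.

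**3. Illustration of bias.** Let a share *p* of a cohort's patient-time belong to patients first diagnosed after index, with *k* times the exacerbation rate of the rest. If the cohort's overall rate is R, the rate after removing them is

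R / (1 − p + pk).

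If both cohorts truly have the same rate and the same *k*, the observed ratio A/B is

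(1 − p_B + p_B·k) / (1 − p_A + p_A·k).

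R = 0.90 per patient-year is a planning rate from Section 9.5. The values of *p* and *k* are assumptions; the documents give neither.

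Equal removal:
- p = 1%, k = 1.5: 0.90/1.005 = 0.896.
- p = 5%, k = 3: 0.90/1.10 = 0.818.
- The ratio stays at 1.00 while the absolute rates fall.

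Unequal removal, true ratio 1.00:

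| Removed from A | Removed from B | k = 1.5 | k = 2 | k = 3 |
|---|---|---|---|---|
| 1% | 3% | 1.010 | 1.020 | 1.039 |
| 3% | 6% | 1.015 | 1.029 | 1.057 |
| 5% | 10% | 1.024 | 1.048 | 1.091 |
| 2% | 10% | 1.040 | 1.078 | 1.154 |

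Worked cell (5% vs 10%, k = 2): 0.90/1.05 = 0.857 and 0.90/1.10 = 0.818; ratio 1.10/1.05 = 1.048. Swapping the cohorts inverts each ratio, and k below 1 also reverses the direction, so the sign is unknown.

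**4. Could removal differ by cohort?** Section 9.9 dates the Taiwanese launch of the fixed-dose tiotropium/olodaterol product to 18 April 2016. From then to 1 August 2019 is about 3.3 years, the longest a patient on that product could have between index and the start of chart review. The plan sets no earliest index date for the other cohorts, so their charts could run longer and leave more time for an excluding diagnosis to appear. This shows a possible route, not that it occurred.

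**The case against.** **The literal reading is not an express instruction.** Section 9.3.3.1 tells sites to check the chart and sets no window in either direction. The asthma example in Section 9.3.2.2 makes sense only if later-diagnosed patients stay in, which suggests the authors meant diagnoses at index. This stands: a reader might infer that the plan orders removal on the follow-up year, but it does not say so. It leaves about 12 hospitals to decide, which creates a risk of inconsistent application.

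**The conflict with the outcome is narrow.** A reader might infer that asthma as an escalation reason must be zero. That holds only if every site applies the literal reading. Asthma is one of three examples ("severe airflow limitation, diagnosis of asthma, worsening exacerbation"); bronchiectasis, cystic fibrosis and lung cancer are not named as reasons. Time to escalation, percentage escalating and other reasons remain observable among the patients kept.

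**No size can be derived.** A reader might assume 5% removed from one cohort and 2% from another, at 2 to 3 times the full-cohort rate. From (1 − pm)/(1 − p), where m is that multiple, the ratio is then multiplied by 0.967 to 0.933, a 3–7% shift to set against a planned 13% effect. The documents do not support this. They give no post-index incidence, no split by cohort and no multiplier. With the multiplier defined against the remaining patients, the same inputs give 1.02/1.05 = 0.971 and 1.04/1.10 = 0.945. The 0.87 in Section 9.5 illustrates the precision of a rate ratio, which is a secondary outcome; it is not a design effect for time to first exacerbation.

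**Censoring limits the effect.** The abstract censors at a switch to ICS, and Section 9.7.1 censors patients who are exacerbation-free when they escalate to ICS. For a patient moved to ICS after an asthma diagnosis, only earlier time and events would count in the primary analysis. This stands, and the illustration does not allow for it.

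**Early diagnoses may show misclassification.** Asthma or ACOS recorded soon after index may mean the COPD label was wrong from the start, so keeping such patients has a cost. This is a fair trade-off, and it is better handled by a declared sensitivity analysis than by an undated rule.

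**Conclusion.** The concern holds as a defect in the eligibility rule. The exclusion is undated in all three places, and it is applied to charts that already contain the whole follow-up year. Followed as written, it selects on post-index information and conflicts with a named example in a secondary outcome; read as applying at index, it may be applied unevenly across sites. Neither conclusion needs an assumed figure.

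The bias itself is conditional. Absolute rates shift if the removed patients' exacerbation risk differs from that of the rest. Between-cohort comparisons shift if removal also differs by cohort, in extent or in the risk of those removed. The range of 0% to about 15% on the rate ratio is illustrative only, has no known direction, ignores censoring at ICS escalation, and says nothing directly about time to first exacerbation. The documents do not establish that the planned comparisons are biased by any particular amount. The wording should still be corrected, because selection of this kind cannot be repaired by matching on baseline variables.

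**What to change.** - In the abstract, Section 9.2.2 and Section 9.3.3.1, limit the exclusion to diagnoses documented on or before the index date.
- Keep patients first diagnosed later in the main analysis, subject to the existing censoring rules, and record the diagnosis and its date on the CRF.
- Add a sensitivity analysis that excludes them, to address possible initial misclassification as COPD.
- This protocol version is dated 25 November 2019 and collection is planned to end on 30 November 2019. If charts have already been screened, ask sites for the date of each excluding diagnosis, so that patients removed only for a post-index diagnosis can be restored.

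The cost is a few words in three places, one dated CRF item and one extra analysis, plus some re-review of charts if screening is done. The downside is that a small number of patients whose COPD label is later revised stay in the main analysis; the sensitivity analysis shows whether they matter.
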